4.0 TREATMENT PLAN**4.1 Treatment Dosage and Administration**

- 4.1.1 400mcg misoprostol or 100mg vitamin B6 placebo administered buccally at least one hour prior to procedure.

4.2 Toxicities and Dosing Delays/Dose Modifications

Given this is a one-time dosing, toxicities will be limited to the immediate intervention period. Any patient who receives treatment on this protocol will be evaluable for toxicity for the entire duration of action of this

medication.

According to published research, serum levels of misoprostol nadir 6 hours following administration and the duration of pharmacologic action is considered to be only 3 hours (3,5). All patients are hospitalized following abdominal myomectomy and laparoscopic such that all patients will be monitored as inpatients for a minimum of 4 hours post-operatively.

4.3 Concomitant Medications/Treatments

None.

4.4 Other Modalities or Procedures

None.

4.5 Duration of Therapy

Pre-operative administration of misoprostol or pyridoxine placebo.

4.6 Duration of Follow Up

Patients will be followed for the duration of their hospital admission following abdominal or laparoscopic myomectomy. Patients will be required to stay a minimum of 4 hours post-surgery. Blood will be drawn right before patient leaves the hospital, post operatively.

4.7 Removal of Patients from Protocol Therapy

Patients will be removed from therapy when any of the criteria listed in Section 5.5 apply. The principal investigator will be notified of any and all patients removed from therapy and the reason for study removal and date the patient was removed will be documented in the Case Report Form. The patient will be followed-up per protocol.

4.8 Patient Replacement

If a patient is removed from the study, an additional patient may be enrolled and randomized to replace them.

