5.4 Removal of Subjects from Study

Patients can be taken off the study treatment and/or study at any time at their own request, or they may be withdrawn at the discretion of the investigator for safety, behavioral or administrative reasons. The reason(s) for discontinuation will be documented and may include:

- 5.5.1** Patient voluntarily withdraws from treatment (follow-up permitted);
- 5.5.2** Patient withdraws consent (termination of treatment and follow-up);
- 5.5.3** Patient is unable to comply with protocol requirements;
- 5.5.4** Patient experiences toxicity that makes continuation in the protocol unsafe;
- 5.5.5** Treating physician judges continuation on the study would not be in the patient's best interest;
- 5.5.6** Patient becomes pregnant (pregnancy to be reported along same timelines as a serious adverse event);
- 5.5.7** Lost to follow-up. If a research subject decides against undergoing abdominal or laparoscopic myomectomy and/or surgical case is cancelled after receiving misoprostol or placebo, the

subject may be considered lost to follow-up.

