7.7 Stopping Rules

This study involves a one-time pre-operative intervention prior to a planned surgical procedure. If a patient develops immediate, intolerable side effects including but limited to emesis, diarrhea, or heavy vaginal bleeding following buccal administration of misoprostol or placebo, therapy will be discontinued.

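### Section 4.8 lets a woman who has already had the single dose be replaced, and nothing in 4.7, 5.4 or 10.3 keeps her in the randomised comparison

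*Combined protocol and SAP*

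**What the plan says.** Section 4.8 is one sentence: "If a patient is removed from the study, an additional patient may be enrolled and randomized to replace them". It sets no condition on dosing status, reason or arm.

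The reasons for removal are numbered 5.5.1 to 5.5.7 but sit under heading 5.4. That section opens "Patients can be taken off the study treatment and/or study at any time at their own request" and adds, as a separate clause, withdrawal by the investigator for safety, behavioural or administrative reasons. The list includes 5.5.4, "Patient experiences toxicity that makes continuation in the protocol unsafe", and 5.5.5, "Treating physician judges continuation on the study would not be in the patient's best interest".

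Section 4.7 uses the same list for a different purpose: "Patients will be removed from therapy when any of the criteria listed in Section 5.5 apply". It then asks for the reason for study removal to be recorded, and ends "The patient will be followed-up per protocol".

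Section 7.7 says that if intolerable effects such as emesis, diarrhea or heavy vaginal bleeding occur "following buccal administration of misoprostol or placebo, therapy will be discontinued". Section 4.2 describes the treatment as one-time dosing.

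Section 10.3 names the tests and models. It does not say which randomised women enter them.

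**The concern.** Once the tablets have been taken there is no further treatment to stop. Removing a dosed woman can then change only whether she is followed and whether her data are used. If she leaves the study and another woman is randomised in her place, the head count is restored but the randomised comparison is not.

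This matters most if removals differ between arms. The triggers in 7.7 closely match the adverse-reaction outcome in section 10.1 (vaginal bleeding, vomiting or diarrhea). Section 1.2 lists all three as misoprostol effects, while section 8.2 lists no side effects for the placebo. At stake are the blood-loss comparison and, if removed women are left out of it, the adverse-effect count under objective 2.2.3.

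**Working it through.** **1. What happens to a dosed woman, by reason for removal**

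| Reason | Section 4.7 | Section 5.4 | Reading |
|---|---|---|---|
| 5.5.1 leaves treatment voluntarily | followed | follow-up permitted | compatible |
| 5.5.2 withdraws consent | followed | follow-up ends | direct conflict |
| 5.5.4 toxicity | followed | silent | ambiguous |
| 5.5.5 physician judgement | followed | silent | ambiguous |
| 5.5.7 surgery cancelled after dosing | followed | may count as lost to follow-up | tension |

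For toxicity and physician judgement the problem is not a contradiction about follow-up. A site cannot tell whether the woman is off treatment or off the study, and 4.8 depends on which it is.

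**2. Whether the analysis plan settles it.** It does not. Section 10.3 has no intention-to-treat or other analysis set.

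**3. Whether losses after surgery are already being made up.** Yes. Section 10.2 raises enrolment from 50 to 70 to cover 9 participants. One of its three reasons is leaving hospital after surgery without a first-postoperative-day value. Those women had their operation, so intraoperative blood loss could have been recorded. The split of the 9 by reason is not given, and neither toxicity nor physician judgement is among the reasons.

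**4. The plan's own figure.** Section 10.2 gives 25 per arm for a 1 SD difference at 90% power. A two-sample t-test at two-sided 0.05 (sidedness is not stated, so this is assumed) needs 22.02, rounded up to 23, per arm. That is close to 25. At the 35 per arm in the Study Summary, power for 1 SD is 98.5%. The point does not depend on these figures; 35 per arm is only the base for the illustration.

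**5. Illustration.** The documents give neither the share removed nor how removed women bleed, so both are assumed. Let r be the share removed from the misoprostol arm only, and d the gap in mean blood loss between removed and kept women, in SD. The true effect is zero, and the arm is refilled to 35 with women like those kept.

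- Full-arm mean = kept mean + r × d, so bias = −r × d (towards misoprostol).
- Standard error = √(2/35) = 0.239 SD.
- Two-sided type I error from the noncentral t with 68 degrees of freedom and noncentrality −r × d / 0.239.

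| r (women of 35) | d = 0.5: bias, type I error | d = 1: bias, type I error |
|---|---|---|
| 3% (1.1) | 0.015 SD, 0.050 | 0.03 SD, 0.052 |
| 5% (1.8) | 0.025 SD, 0.051 | 0.05 SD, 0.055 |
| 10% (3.5) | 0.05 SD, 0.055 | 0.10 SD, 0.070 |
| 15% (5.2) | 0.075 SD, 0.061 | 0.15 SD, 0.095 |

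If replacements come from the full population and none of them is removed, the bias shrinks to r × d × (1 − r). In the last cell that is 0.15 × 1 × 0.85 = 0.13 SD. If similar women are removed equally from both arms, it is zero. If removed women bleed less than the others, the sign reverses.

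**The case against.** The strongest reply is that this is a permissive rule in a double-blind trial. Section 4.8 allows replacement without requiring it. Section 7.7 covers both arms, and replacements are randomised afresh, so they need not join the arm that lost a woman. All of this stands. A reader might infer that outcome-related removal from one arm is built into the plan; the text supports only that it is not prevented.

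Other stronger readings also fail:

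- *High-loss cases can be dropped after surgery.* In 5.4 the words on timing attach to the patient's own request, and investigator withdrawal is limited to stated kinds of reason. No section describes removal once blood loss is known.
- *Sections 4.7 and 5.4 contradict each other on toxicity.* They do so directly only for withdrawal of consent.
- *Section 7.7 removes women from the study.* It ends therapy. The step from there to 4.8 is left open.
- *The adverse-effect rate will be understated.* Section 4.2 keeps every treated woman assessable for toxicity, and section 7.2 monitors every patient with an adverse event. Under-counting follows only if removed women are left out of the 2.2.3 analysis.
- *Heavy bleeding as a trigger biases the primary endpoint.* Vaginal bleeding after the tablets is not intraoperative loss.

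The expected number of removals may also be small. The discontinuation figure for diarrhea in section 7.1.4 is 2%, from repeated dosing, which would be 0.02 × 35 = 0.7 women. The same section reports no significant difference from placebo for vomiting.

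These replies limit the size and certainty of the harm. They do not supply the missing rule on who is replaced and who is analysed.

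**Conclusion.** The point holds as a gap in the rules. Replacement after dosing is allowed, the status of a removed woman is unclear, and the analysis plan does not retain her. Differential exclusion is therefore possible, and there is a plausible reason for it, because the triggers in 7.7 are listed effects of the active drug.

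The size and direction of any bias in blood loss cannot be derived from the documents. The range of 0.015 to 0.15 SD, with type I error from 0.05 to about 0.095, rests wholly on three assumptions: removals in one arm only, a share of 3% to 15%, and removed women bleeding 0.5 to 1 SD more. Even the top of that range is 15% of the 1 SD difference the trial is designed to detect. It is worth correcting because the correction is cheap, not because a large bias has been shown.

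**What to change.** - **4.8:** limit replacement to women who received no study drug. Count any other extra enrolment as additional participants, not as substitutes.
- **4.7, 4.8 and 5.4:** reconcile them, including the reference to a Section 5.5 that has no heading, so that ending treatment does not end data collection. Only withdrawal of consent ends further collection, and data up to that date are kept.
- **10.3:** analyse all dosed women who have surgery as randomised, using the chart data available. Count all dosed women for adverse effects, including those whose surgery is cancelled. Report removals by arm with reasons. Square this wording with 3.2.7, which separately excludes some operated women from analysis.

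The clinical stopping and withdrawal criteria in 5.4 and 7.7 are left unchanged.

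The cost is protocol wording, since the outcomes are routine chart data. The downside is that women who tolerate the drug poorly stay in the comparison, so the result may be slightly less favourable to misoprostol.

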5.0 STUDY PROCEDURES

5.1 Screening/Baseline Procedures

Assessments performed exclusively to determine eligibility for this study will be done only after obtaining informed consent. Assessments performed for clinical indications (not exclusively to determine study eligibility) may be used for baseline values even if the studies were done before informed consent was obtained.

All screening procedures must be performed within ninety days of registration unless otherwise stated. The screening procedures include:

5.1.1 Informed Consent

Will be obtained for all potentially eligible participants. Please see attached Informed Consent documents, including eConsent, which will be sent through REDCap.

5.1.2 Medical history

Complete medical, surgical, gynecologic and obstetrical history, medications, allergies, social and family history including and history of prior myomectomy and personal or family history of blood dyscrasias,

coagulopathy and bleeding disorders.

5.1.3 Demographics

Age, gender, race, ethnicity, gravidity, parity.

5.1.4 Review subject eligibility criteria

Refer to section 3.0.

5.1.5 Review previous and concomitant medications

5.1.6 Physical exam including vital signs, height and weight

Vital signs (temperature, pulse, respirations, blood pressure), height, weight.

5.1.7 Adverse event assessment

Baseline adverse events will be assessed. See section 6 for Adverse Event monitoring and reporting.

5.1.8 Baseline Hemoglobin

Baseline serum hemoglobin will be determined for all patients.

5.1.9 Pregnancy test (for reproductive age females)

See section 3.1.6.1 for definition.

5.1.10 Other

*Note: Aside from signing of informed consent, all of the above information will be garnered from existent medical records. No additional physical examination, history taking or laboratory testing will be required of study participants.

5.2 Procedures During Treatment

Administration of 400mcg Misoprostol or 100mg Pyridoxine (placebo).

5.3 Follow-up Procedures

None.

5.4 Removal of Subjects from Study

Patients can be taken off the study treatment and/or study at any time at their own request, or they may be withdrawn at the discretion of the investigator for safety, behavioral or administrative reasons. The reason(s) for discontinuation will be documented and may include:

- 5.5.1** Patient voluntarily withdraws from treatment (follow-up permitted);
- 5.5.2** Patient withdraws consent (termination of treatment and follow-up);
- 5.5.3** Patient is unable to comply with protocol requirements;
- 5.5.4** Patient experiences toxicity that makes continuation in the protocol unsafe;
- 5.5.5** Treating physician judges continuation on the study would not be in the patient's best interest;
- 5.5.6** Patient becomes pregnant (pregnancy to be reported along same timelines as a serious adverse event);
- 5.5.7** Lost to follow-up. If a research subject decides against undergoing abdominal or laparoscopic myomectomy and/or surgical case is cancelled after receiving misoprostol or placebo, the

subject may be considered lost to follow-up.

6.0 Response Criteria

Clinically-documented intraoperative blood loss.

6.1 Safety/Tolerability

All patients will be closely monitored by physician and nursing staff in the operating room and post-operative recovery area for the full duration of action of the active medication. Misoprostol is largely considered a safe, well-studied medication (10). The risk profile may be even more favorable when a single dose of misoprostol is administered (11).

The placebo medication, pyridoxine (Vitamin B6), is a safe nutritional supplement with no known side effects of a one-time dose. Additionally, it is absorbed in the jejunum such that absorption when buccally administered (12).

7.0 ADVERSE EVENTS

7.1 Experimental Therapy

For the most recent safety update, please refer to the current Investigator's Brochure or Study Agent Prescribing Information. The following information is taken from the FDA website (10).

7.1.1 Contraindications

Pregnancy, history of allergy to prostaglandins or Vitamin B6.

7.1.2 Special Warnings and Precautions for Use

In pregnant women, cytotec can cause birth defects, abortion or premature birth. Uterine rupture has been reported when cytotec has been administered to pregnant women to induce labor or to induce abortion beyond the 8th week of pregnancy. Patients should be advised that cytotec should not be given to others due to its abortifacient properties.

Cytotec may be prescribed if the patient:

- has had a negative serum pregnancy test within 2 weeks prior to beginning therapy.
- is capable of complying with effective contraceptive measures.
- has received both oral and written warnings of the hazards of misoprostol, the risk of possible contraception failure, and the danger to other women of childbearing potential should the drug be taken by mistake.
- will begin Cytotec only on the second or third day of the next normal menstrual period.

WARNING for off-label uses:

For hospital use only if misoprostol were to be used for cervical ripening, induction of labor, or for the treatment of serious post-partum hemorrhage, which are outside of the approved indication.

7.1.3 Interaction with other medications

Misoprostol is a renally-cleared medication and does not affect the hepatic mixed function oxidase (cytochrome P-450) enzyme systems in animals.

Drug interaction studies between misoprostol and several nonsteroidal anti-inflammatory drugs showed no effect on the kinetics of ibuprofen or diclofenac, and a 20% decrease in aspirin AUC, not thought to be clinically significant. Pharmacokinetic studies also showed a lack of drug interaction with antipyrine and propranolol when these drugs were given with misoprostol. Misoprostol given for 1 week had no effect on the steady state pharmacokinetics of diazepam when the two drugs were administered 2 hours

apart. The serum protein binding of misoprostol acid is less than 90% and is concentration-independent in the therapeutic range.

7.1.4 Adverse Reactions

The FDA reports the following possible side effects with the active medication (Misoprostol):

Gastrointestinal: In subjects receiving Cytotec 400 or 800 mcg daily in clinical trials, the most frequent gastrointestinal adverse events were diarrhea and abdominal pain. The incidence of diarrhea at 800 mcg in controlled trials in patients on NSAIDs ranged from 14-40% and in all studies (over 5,000 patients) averaged 13%. Abdominal pain occurred in 13-20% of patients in NSAID trials and about 7% in all studies, but there was no consistent difference from placebo.

Diarrhea was dose related and usually developed early in the course of therapy (after 13 days), usually was self-limiting (often resolving after 8 days), but sometimes required discontinuation of Cytotec (2% of the patients). Rare instances of profound diarrhea leading to severe dehydration have been reported.

Patients with an underlying condition such as inflammatory bowel disease, or those in whom dehydration, were it to occur, would be dangerous, should be monitored carefully if Cytotec is prescribed.

Gynecological: Women who received Cytotec during clinical trials reported the following gynecological disorders: spotting (0.7%), cramps (0.6%), hypermenorrhea (0.5%), menstrual disorder (0.3%) and dysmenorrhea (0.1%). Postmenopausal vaginal bleeding may be related to Cytotec administration. If it occurs, diagnostic workup should be undertaken to rule out gynecological pathology. Research studies in obstetrics and gynecology also identify possible side effects of diarrhea, fever and shivering (4,6,7).

Elderly: There were no significant differences in the safety profile of Cytotec in approximately 500 ulcer patients who were 65 years of age or older compared with younger patients.

Additional adverse events which were reported are categorized as follows:

In clinical trials, the following adverse reactions were reported by more than 1% of the subjects receiving Cytotec and may be causally related to the drug: nausea (3.2%), flatulence, (2.9%), headache (2.4%), dyspepsia (2.0%), vomiting (1.3%), and constipation (1.1%). However, there were no significant differences between the incidences of these events for Cytotec and placebo.

Causal relationship unknown: The following adverse events were infrequently reported. Causal relationships between Cytotec and these events have not been established but cannot be excluded:

Body as a whole: aches/pains, asthenia, fatigue, fever, rigors, weight changes.

Skin: rash, dermatitis, alopecia, pallor, breast pain.

Special senses: abnormal taste, abnormal vision, conjunctivitis, deafness, tinnitus, earache.

Respiratory: upper respiratory tract infection, bronchitis, bronchospasm, dyspnea, pneumonia, epistaxis.

Cardiovascular: chest pain, edema, diaphoresis, hypotension, hypertension, arrhythmia, phlebitis, increased cardiac enzymes, syncope.

Gastrointestinal: GI bleeding, GI inflammation/infection, rectal disorder, abnormal hepatobiliary function, gingivitis, reflux, dysphagia, amylase increase.

Hypersensitivity: anaphylaxis

Metabolic: glycosuria, gout, increased nitrogen, increased alkaline phosphatase.

Genitourinary: polyuria, dysuria, hematuria, urinary tract infection.

Nervous system/Psychiatric: anxiety, change in appetite, depression, drowsiness, dizziness, thirst, impotence, loss of libido, sweating increase, neuropathy, neurosis, confusion.

Musculoskeletal: arthralgia, myalgia, muscle cramps, stiffness, back pain.

Blood/Coagulation: anemia, abnormal differential, thrombocytopenia, purpura, ESR increased.

7.2 Adverse Event Monitoring

Adverse event data collection and reporting, which are required as part of every clinical trial, are done to ensure the safety of Subjects enrolled in the studies as well as those who will enroll in future studies using similar agents. Adverse events are reported in a routine manner at scheduled times during a trial. Additionally, certain adverse events must be reported in an expedited manner to allow for optimal monitoring of patient safety and care.

All patients experiencing an adverse event, regardless of its relationship to study drug/device, will be monitored until:

- Ø the adverse event resolves or the symptoms or signs that constitute the adverse event return to baseline;
- Ø any abnormal laboratory values have returned to baseline;
- Ø there is a satisfactory explanation other than the study drug for the changes observed; or
- Ø death.

7.3 Definitions

7.3.1 Definition of Adverse Event

An adverse event (AE) is any untoward medical occurrence in a patient receiving study treatment and which does not necessarily have a causal relationship with this treatment. An AE can therefore be any unfavorable and unintended sign (including an abnormal laboratory finding), symptom, or disease temporally associated with the use of an experimental intervention, whether or not related to the intervention.

7.3.2 Severity of Adverse Events

The severity of an AE is graded as follows:

Mild (grade 1): the event causes discomfort without disruption of normal daily activities.

Moderate (grade 2): the event causes discomfort that affects normal daily activities.

Severe (grade 3): the event makes the patient unable to perform normal daily activities or significantly affects his/her clinical status.

Life-threatening (grade 4): the patient was at risk of death at the time of the event.

Fatal (grade 5): the event caused death.

7.3.3 Serious Adverse Events

A “serious” adverse event is defined in regulatory terminology as any untoward medical occurrence that:

7.3.3.1 Results in death.

If death results from (progression of) the disease, the disease should be reported as event (SAE) itself.

7.3.3.2 Is life-threatening.

(the patient was at risk of death at the time of the event; it does not refer to an event that hypothetically might have caused death if it were more severe).

7.3.3.3 Requires in-patient hospitalization or prolongation of existing hospitalization for ≥ 24 hours.

7.3.3.4 Results in persistent or significant disability or incapacity.

